6.2.3 Elimination criteria

- Withdrawal of the consent letter under information.
- Presentation of a serious adverse event.
- No tolerability or hypersensitivity to any of the compounds used during the tests (fluorescein, green lysine, tetracaine)
- No tolerability or hypersensitivity to any of the investigational drugs.
- Adherence <50% determined by the diary of the subject, of the established dose of the pharmacological intervention in any of the visits.

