6.3.2.2 Procedure to determine adherence

The final adhesion will be determined by the sponsor by means of the weight of the bottle.

Before delivering the medication to the research center, the weighing of the bottles to be delivered must be carried out. After the return of the medication by the center will be weighing. The weighing will be carried out according to the procedures regulated by the sponsor.

The adhesion will be calculated considering: the weight of the empty bottle, the weight of the drop, the weight of the bottle with the content, the calculation of the total of drops to be applied during the entire time of intervention and the total weight of the drops applied. The following simplified formula will be used:

$$Ad = \frac{(P_i - P_f)100}{P_T}$$

Where:

Ad = adhesion

P_i = weight of the bottle delivered to the subject at the start

P_f = weight of the bottle returned by the subject

P_T = weight of the posology indicated for the intervention.

$$P_T = (P_g)G$$

Where:

P_g = weight of the drop of the intervention, determined by the department of research and development

G = number of drops indicated for the intervention.

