8.3 Statistical methodology

8.3.1 Analysis of primary and secondary outcome variables.

The statistical analysis will be carried out by personnel from Sophia Laboratories, S.A. of C.V The statistical program SPSS version 19 (IBM Corporation, Armonk, NY, USA) will be used.

The designated personnel will be blinded to the intervention groups. The coding will be done using consecutive numbers for each intervention group.

The data will be collected and sorted in an excel sheet. Later they will be exported to the platform of the SPSS program. The variables will be categorized according to their nature.

The result of the continuous quantitative variables will be presented in measures of central tendency: media, standard deviation and ranges. **See Table 6.** Scales to be used

The normal distribution of the results will be obtained by the Kolmogorov-Smirnov test.

The statistical analysis of the continuous **quantitative variables** to find significant differences (p) will be the following:

- Intra-group analysis: Wilcoxon rank test.
- Inter-group analysis: Mann-Whitney U test.

The level of difference to consider significance will be of an alpha of 0.05 or less.

The result of nominal and ordinal qualitative variables will be presented in frequencies, proportions and percentages. See table 1 (section 6.4.3).

The statistical analysis to identify significant differences of the **qualitative variables** will be done by creating 2x2 contingency tables and will be done as follows:

- Intra-group difference: McNemar test.
- Difference between groups: test χ^2 (Chi-square) of Pearson.

The level of difference to consider significance will be of an alpha of 0.05 or less.

For the reporting of adverse events all eyes of those participants who were randomly assigned to an intervention group after the baseline visit will be considered. The results will be expressed in number of cases (eyes).

The final report of the results will be shown in tables or graphs, as appropriate.

It will be considered that the investigational drug is safe and tolerable when there are no clinical and statistical differences in all the variables of primary outcome, with respect to its comparators.

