Those subjects who comply with an adherence greater than 60% will be included in the statistical analysis to meet the objective of the study. It was considered that from the minimum dose necessary to obtain a pharmacological effect and the presence of adverse events (exposure) is sufficient to fulfill the general objective of the design, according to the pharmacological characteristics of the product under investigation.

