8.3.3 Population analysis and management of missing data

An intention-to-treat analysis will be carried out, where the data of the participants who have completed the final visit will be included.

9. Methods Monitoring

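### The analysis set called intention-to-treat is a completer set, and a separate 60% adherence rule also applies, so Visit 1 data from subjects who stop for intolerance can leave the primary comparisons

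*Combined protocol and SAP*

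**What the plan says.** Section 8.3.3, the only section on analysis populations and missing data, consists of one rule: "An intention-to-treat analysis will be carried out, where the data of the participants who have completed the final visit will be included". It gives no rule for handling missing values.

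Section 8.3.1 adds a second condition: "Those subjects who comply with an adherence greater than 60% will be included in the statistical analysis to meet the objective of the study". It justifies this by saying that such exposure is enough to judge effects. Neither section refers to the other.

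Section 8.3.1 makes one exception. For reporting adverse events, "all eyes of those participants who were randomly assigned to an intervention group after the baseline visit will be considered". It also sets the decision rule: PRO-174 counts as "safe and tolerable when there are no clinical and statistical differences in all the variables of primary outcome", relative to the comparator.

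Section 6.2.3 removes subjects for "No tolerability or hypersensitivity to any of the investigational drugs", for "Presentation of a serious adverse event", and for "Adherence <50% determined by the diary of the subject, of the established dose of the pharmacological intervention in any of the visits". Section 6.5.1.3 has a decision at Visit 1 on whether the subject continues. Under section 8.1.1, when a missed visit cannot be rearranged, the minimum data are adverse events and the reason for leaving.

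**The concern.** Tolerability is a primary outcome, and failing to tolerate the drops is a way out of its analysis. A subject could report severe burning at Visit 1, stop for that reason, and be absent from the burning comparison although the score is already in the case report form. The loss is then related to the outcome. Because success is defined as finding no differences, removing affected subjects mainly from the PRO-174 arm would make the favourable conclusion easier to reach. The exposure argument in section 8.3.1 does not cover subjects whose exposure is low because they did not tolerate the product.

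The intention-to-treat label adds to the problem, since a reader of the final report would assume that all randomised subjects were analysed.

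**Working it through.** The plan gives no figure on this point to reproduce. The inputs are the dosing in section 1 (8 applications a day on days 1 and 2, then 4 a day on days 3 to 7), the visit windows in section 6.4.4 (Visit 1 on day 3 ± 1, final visit on days 8 to 10), and 15 subjects per arm (section 6.6.1).

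**Step 1: which variables have a Visit 1 value.** Sections 6.4.1.1 and 6.4.1.2 list the primary variables. By section 6.4.4, those examined at Visit 1, other than adverse events, are pressure, visual ability, staining, hyperemia, chemosis, burning, foreign body sensation and itching. The comfort index and post-treatment laboratory tests are not taken at Visit 1, so no Visit 1 data on them can be lost.

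**Step 2: adherence of a subject who takes every dose and then stops.** Full course: 8 × 2 + 4 × 5 = 36 applications. Exceeding 60% of 36 (21.6) needs at least 22.

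| Stops at end of | Applications | Share of full course | 60% rule, full course | 60% rule, measured to date | Section 8.3.3 rule |
|---|---|---|---|---|---|
| Day 2 | 16 | 16/36 = 44.4% | fails | 16/16 = 100%, passes | in only if final visit made |
| Day 3 | 20 | 20/36 = 55.6% | fails | 20/20 = 100%, passes | in only if final visit made |
| Day 4 | 24 | 24/36 = 66.7% | passes | 24/24 = 100%, passes | in only if final visit made |

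The full-course denominator is the one in section 6.3.2.2, which uses "the calculation of the total of drops to be applied during the entire time of intervention". Section 8.3.1 does not say which measure it means.

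**Step 3: the two cut-offs.** Half of 36 is 18. If both cut-offs used the same full-course measure, a subject with 18 to 21 applications (50.0% to 58.3%) would not be eliminated under section 6.2.3 but would fail the 60% rule. That common measure is an assumption: section 6.2.3 uses the diary at any visit, section 6.3.2.2 uses bottle weight, and section 8.3.1 names neither. A full-course denominator cannot be intended for the diary rule at Visit 1, because a perfect user seen at the end of day 2 would score 44.4% and be eliminated.

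**Step 4: sensitivity of the test.** Pearson chi-square as planned, without continuity correction: χ² = N(ad − bc)² / (product of the four margins). The counts are illustrative.

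- 4/15 v 0/15: 30 × (4 × 15)² / (15 × 15 × 4 × 26) = 4.615, p = 0.032.
- One affected subject removed, 3/14 v 0/15: 29 × (3 × 15)² / (14 × 15 × 3 × 26) = 3.585, p = 0.058.
- All four removed, 0/11 v 0/15: no difference is visible.
- Counted by eye, with two subjects affected in both eyes: 4/30 v 0/30 gives p = 0.038. With one of them removed, 2/28 v 0/30 gives p = 0.136. This treats eyes as independent.
- Away from the boundary, 5/15 v 0/15 has p = 0.014. It stays below 0.05 after losing one (4/14, p = 0.026) or two (3/13, p = 0.049), but not three (2/12, p = 0.100).
- With 1, 2 or 3 of 15 affected and none in the comparator, the complete data would not be significant either when counted by subject (p = 0.31, 0.14, 0.068).

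**The case against.** Adverse events are themselves a primary variable, and success requires no difference in every primary variable. Intolerance recorded as an adverse event stays in the report for all randomised eyes, with eye, intensity, relationship and drug withdrawal (sections 9.3.1.1 and 9.3.1.3). An excess on PRO-174 could by itself defeat the favourable conclusion. This stands as a partial safeguard, with two limits. The adverse-event record does not carry symptom scores, Efron and Oxford grades or pressure values. The exception is also worded for reporting, so it is unclear whether the adverse-event test uses all randomised eyes.

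The p-values sit at the significance boundary. At the 7.3% adverse-event rate in section 6.6.1, 15 × 0.073 = 1.1 subjects per arm are expected, and four or more has a probability of about 2%. This also stands: the examples show fragility, not a forecast. Milder symptoms could be commoner, but the plan gives no rate for them. The chi-square examples say nothing about pressure, which is tested by Mann-Whitney.

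A reader might infer that the two rules stack, so that anyone at 50 to 60% adherence is always excluded. The documents do not support that. Sections 8.3.1 and 8.3.3 may describe two sets, and such a subject who attends the final visit would then be in the section 8.3.3 set. Different cut-offs for continuing and for analysis are not in themselves an error.

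**Conclusion.** The concern holds in this form: section 8.3.3 mislabels a completer set, its relation to the 60% rule is undefined, and either rule can drop collected Visit 1 data for reasons tied to the outcome. The day 3 exclusion at 55.6% assumes the full-course measure. If adherence is measured to date, exclusion depends only on a missing final visit. A subject who stops after day 4 passes the 60% rule but is outside the section 8.3.3 set without that visit.

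The direction of bias, toward finding no differences, assumes that such stops are more frequent on PRO-174. The number affected is not computable from the documents. With 15 per arm, one lost subject can reverse a borderline result but not a clear one. A reader might infer that the plan will hide intolerance altogether. The documents do not support that, because adverse-event reporting keeps everyone randomised. The change should be made, since it corrects a stated rule at little cost.

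**What to change.** Amend sections 8.3.1 and 8.3.3 as follows:

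- Define the primary safety and tolerability set as all randomised subjects who received at least one dose, whatever their adherence, elimination or withdrawal. State that the adverse-event test uses this set too.
- Compare arms by visit (Visit 1 and final visit) with all collected values. For signs and symptoms, also compare the worst post-baseline grade. This is needed because early stoppers may have no final-visit value.
- Report by arm the number without a final visit and the reasons.
- Keep completers with adherence above 60% as a sensitivity set under its own name, and state which adherence measure applies.

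The cost is wording and slightly more analysis, with no added visit. The comfort index and post-treatment laboratory tests remain missing for subjects without a final visit. Subjects with low exposure for unrelated reasons may dilute a difference, which the sensitivity set would show.

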9.1 Data monitoring

Monitoring visits by a site monitor from Sophia Laboratories, S.A. of C.V are intended to confirm that the studies sponsored by Sophia Laboratories, S.A. of C.V they are conducted in accordance with the ethical principles that have their origin in the Declaration of Helsinki, which are consistent with Good Clinical Practices and with the applicable regulatory requirements; verifying its continuous compliance with the protocol, amendment or amendments. The monitor will review the accounting records of the product under investigation, and verify that site personnel and facilities remain adequate to carry out the study.

The researcher must ensure that they have sufficient time, space and qualified personnel for the monitoring visits.

In order to carry out the monitoring review, it is mandatory to provide direct access to all source data and those related to the study site. The monitor will conduct a review of the CRF and a Verification of Source Documents (VDF). By VDF means the verification of the records in the CRF through its comparison with the source data that the researcher will make available for this purpose.

Regarding the CRF, the monitor will mark in each visit the screens completed and approved in case of use of electronic platform.

In accordance with the applicable regulations, Good Clinical Practices, and the procedures of Sophia Laboratories, S.A. of C.V. The monitors of Sophia Laboratories, S.A. of C.V. they will contact the site before the start of the study to review with the staff the protocol, the regulatory, ethical requirements and from Sophia Laboratories, S.A. of C.V.

Sophia Laboratories, S.A. of C.V. will monitor the study to verify, among other things, that:

- The data is authentic, correct and complete.
- The safety and rights of the subjects are being protected.
- The study is being conducted in accordance with the currently approved protocol, any other study agreement, Good Clinical Practices and all applicable regulatory requirements.
-

The investigator and the head of the medical institution (when applicable) agree to allow the monitor to have direct access to all relevant documents.

Study monitoring visits will be conducted at regular intervals, depending on the recruitment rate, under the arrangements between the investigator and the sponsor. All information related to these visits will be handled as strictly confidential.

Upon completion or early termination of the study, the monitor will carry out site closure activities with the investigator or site staff, as appropriate, in accordance with applicable regulations, Good Clinical Practices, and Sophia Laboratory procedures. , SA of C.V.

After the study is closed, the researcher must keep all study records on the site in a safe place. Records should be maintained to allow easy and timely recovery, when necessary (for example, in an audit or inspection). Sophia Laboratories, S.A. of C.V. will inform the investigator / institution the period of time they will have to retain these records, in order to comply with all applicable regulatory requirements. Nevertheless, the investigator / institution must seek the written approval of the sponsor before proceeding to the elimination of these records. The minimum retention time will satisfy the most stringent standard applicable to that site for the study, in accordance with the provisions of the PCBs, any institutional requirements or the applicable laws or regulations, or the standards / procedures of Sophia Laboratories, S.A. of C.V.

The researcher / institution must notify Sophia Laboratories, S.A. of C.V. Of any change in file arrangements including, without limitation, the following: file in an off-site facility, ownership transfer of records in the event the investigator leaves the site.

9.2 Preliminary analysis and early termination of the study.

The partial analysis described in section 6.5 and 8.3.2 will allow the sponsor to make a decision about the early termination of the study in the event that the safety of the participants is compromised.

The early termination of the study will be considered in the following cases:

1. Presence of serious adverse events in more than 5% of the participants in each intervention group.
2. The competent authority (COFEPRIS) considers it for security alerts.
3. According to the PCBs, if the CEI considers it pertinent.
4. The Sponsor determined it for convenience or eventualities such as: economic support, manufacturing errors, etc.
5. Less recruitment to the projected.

In case the decision is the early termination of the clinical study, all the research centers will be informed within the first 24 hours by the available communication channels. Likewise, the corresponding authority in each country will be informed (if applicable) and the Ethics Committees involved.

Each research center has the obligation to inform the subjects that participate in the clinical study in a period no longer than 24 hours, after receiving the information from the sponsor. You must inform all the subjects involved in any phase of the study.

The result of the preliminary evaluation will be in charge of the Clinical Operations Management and the Medical Management of Sophia Laboratories, S.A. of C.V., which will have the faculty to determine the fate of the present protocol, as they deem convenient.

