6.6 Sample size

A total size of 30 subjects is estimated, distributed in intervention groups [15 subjects (30 eyes) per group]

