7.4.1 Opening of blinding

Blinding may be opened in the following cases:

1. Presence of a serious adverse event.
2. Safety alarm due to the use of the drugs under study.

3. In case the sponsor determines it for any security reason or other reason that it considers pertinent.

8. Methods Collection, administration and data analysis

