- D. in the research site or in the hospital with the greatest resolving power (1st, 2nd or 3rd level of medical attention). In such a way that, in case the patient is sent by the Investigator to a hospital, he / she attends by means of a reference system, it can be with an identification card that the patient belongs to the present investigation and there is an official number or folio, which pertains to the emergency care agreement with the health institution with the greatest resolving power, or a medical reference note issued by the principal investigator, so that appropriate care is given to the participating patient. It should be noted that the Study Sponsor, Sophia Laboratories, S.A. C.V., will pay the expenses for the medical care of the participating patient, only if the adverse event, adverse reaction or suspected adverse reaction to medication is associated or found in relation to the investigational product or investigational drug.
- E. Taking the clinical information collected, either during the care provided at the research site or provided by the treating physician (s) in the hospital, the principal investigator records the adverse event, suspected reaction adverse or adverse reaction to medication in your clinical note of the clinical record, indicating the seriousness, intensity (mild, moderate or severe), relationship with the product or drug under investigation, as well as:
- F. The migration of the relevant data to the case report format and to its respective adverse event section; noting the pertinent information, already referred to in section 9.3.1.1., this in virtue of the fact that in cases of serious adverse events, which must be notified in less than 24 hours after the moment in which the principal investigator has knowledge of the same, the clinical monitor of the study is informed, so that in turn he / she informs the Scientific Committee and the Pharmacovigilance Department of the sponsor and later he / she informs the Research Ethics Committee. Regarding non-serious adverse events, these will be recorded and adequately addressed and the corresponding regulatory entity will be informed about the safety profile of the product under investigation or investigational medication in the final report of the clinical trial.

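### Early-termination criterion 1 says 'each' group: read literally it needs both arms above 5%, so 5/15 v 0/15 would not meet it; it should say 'either'

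*Combined protocol and SAP*

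**What the plan says.** Section 9.2 introduces five grounds with "The early termination of the study will be considered in the following cases". The first is "Presence of serious adverse events in more than 5% of the participants in each intervention group". It is the only numerical safety threshold at study level; no count and no derivation are given. Section 6.6 sets the group size at "15 subjects (30 eyes) per group".

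The same section says that a partial analysis lets the sponsor decide on "early termination of the study in the event that the safety of the participants is compromised". It places that analysis in sections 6.5 and 8.3.2, but neither contains a by-group rule: 6.5 holds visit procedures and the study diagram, and 8.3.2 plans no further analyses unless a specific safety question arises.

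Other provisions bear on a serious event:

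- The competent authority and the ethics committee are separate grounds for termination (9.2).
- Sponsor management receives the preliminary evaluation, "which will have the faculty to determine the fate of the present protocol, as they deem convenient" (9.2).
- Section 9.3.1.3 provides for rapid reporting "in cases of serious adverse events, which must be notified in less than 24 hours" of the investigator learning of them, to the sponsor and then to the ethics committee.
- "Presence of a serious adverse event" is a ground for unblinding (7.4.1).

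**The concern.** The trial compares a new levofloxacin solution with a marketed ciprofloxacin solution in healthy volunteers. If one product causes serious harm and the other does not, the events fall mainly or wholly in one group. On its literal wording criterion 1 cannot be met when the other group has no events, however many occur in the first: even 15/15 v 0/15 falls outside it. One event in each group, a much weaker signal, is enough.

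What is at stake is whether the sponsor and the ethics committee can tell that the stated criterion has been reached. The two possible readings give opposite answers whenever serious events occur in one group only.

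**Working it through.** **Inputs.** The threshold is more than 5% (section 9.2) and the group size is 15 (section 6.6). The plan derives no figure for this criterion, so there is none to reproduce. The documents give no all-cause serious-event rate for healthy volunteers, so every rate below is an assumption.

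**Step 1: the percentage as a count.** 0.05 × 15 = 0.75, so the smallest count above 5% is 1 (1/15 = 6.7%). The same holds at the 13 per group that section 6.6.1 requires before losses (1/13 = 7.7%).

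**Step 2: the two readings on given outcomes.** This step needs no assumed rate.

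| Subjects with a serious event | Pooled | Literal (both groups above 5%) | Per group (either above 5%) |
|---|---|---|---|
| 1/15 v 1/15 | 2/30 = 6.7% | met | met |
| 1/15 v 0/15 | 1/30 = 3.3% | not met | met |
| 5/15 v 0/15 | 5/30 = 16.7% | not met | met |

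**Step 3: how often the readings differ when the groups have the same rate.** Let p be the true rate per subject in each group, with 15 observed per group and subjects independent.

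- P(at least one event in a group) = 1 − (1 − p)^15
- Literal: [1 − (1 − p)^15]²
- Either: 1 − (1 − p)^30

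| Assumed p | Literal | Either | Readings disagree |
|---|---|---|---|
| 0.1% | 0.02% | 3.0% | 2.9% |
| 0.5% | 0.5% | 14.0% | 13.4% |
| 1% | 2.0% | 26.0% | 24.1% |

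At p = 1%, for example, 1 − 0.99^15 = 0.1399. The literal criterion is then met with probability 0.1399² = 0.0196, the other reading with 1 − 0.99^30 = 0.2603, and the difference is 0.2407. The 'either' column is also the cost of the fix: how often a review would be prompted with no difference between products.

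**Step 4: a one-group signal.** With rates p1 and p2, let P1 and P2 be the chances of at least one event in each group. Literal = P1 × P2; either = 1 − (1 − P1)(1 − P2).

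- 10% v 1%: P1 = 0.7941, P2 = 0.1399. Literal 11.1%, either 82.3%.
- 20% v 1%: P1 = 0.9648, P2 = 0.1399. Literal 13.5%, either 97.0%.
- Any rate v 0%: literal 0%.

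These rates are deliberately high and show only the direction of the effect.

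**The case against.** **The wording may be a translation artefact.** The English is rough throughout, and the phrase can be read as a percentage calculated within each group and not pooled. A rule that ignored 15/15 v 0/15 is hard to credit as intended. This stands, and it means the literal reading cannot be called the sponsor's intention. It does not remove the need for the edit, because no other section says which reading applies.

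**Nothing practical turns on the word.** Termination is only considered, never automatic. The sponsor can act whenever safety is compromised, and the ethics committee and the authority can act independently. Five serious events in one group would each already have been notified, with unblinding available. This also stands, and it sets the severity. A reader might infer that the study could not be stopped for harm confined to one group; these provisions show otherwise.

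**Serious events should be very rare here.** Section 5.3.1.4 reports a phase IV levofloxacin study with a safety population of 6,686 and no serious reaction. By the rule of three, an approximate 95% upper bound is 3/6,686 = 0.045%. At that rate in both groups, 'either' is met in 1 − (1 − 0.00045)^30 = 1.3% of trials. The figure concerns adverse reactions in patients, not all-cause events in volunteers, so it is only a guide. It does make the 10% and 20% rates in step 4 illustrations, not expectations.

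**Eliminated subjects.** Because "Presentation of a serious adverse event" is an elimination criterion (6.2.3), and section 8.3.3 analyses those who completed the final visit, a reader might infer that affected subjects drop out of the count. The documents do not support that: section 8.3.1 reports adverse events for all participants assigned to a group after the baseline visit.

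**Conclusion.** The point holds as a low-severity correction to a stated safety threshold. On its literal wording, criterion 1 needs at least one affected subject in both groups, and so is not met by 5/15 v 0/15. That conclusion rests only on the wording and on 15 per group.

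How often the ambiguity would matter depends on rates that the documents do not supply. With equal rates, the readings disagree in 2.9% of trials at 0.1% per group and 24.1% at 1%; the phase IV experience suggests the lower end or below. The plan does not lack a way to stop for a one-group signal. What it lacks is a criterion that says unambiguously when such a signal has reached the stated level.

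**What to change.** Reword criterion 1 in section 9.2 along these lines:

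> *Serious adverse events in more than 5% of the randomised participants in either intervention group (with 15 per group, 1 or more subjects); this prompts a termination review, not an automatic stop.*

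This keeps the plan's own 5% and states the count that it implies. At a count of one, 'either group' is the same as one or more of all 30 subjects, so the check needs no information by group and no unblinding.

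The change is to protocol wording only, with no extra data, visits or subjects. The downside is that any single serious event, whatever its cause, prompts a review: about 3% of trials at an assumed 0.1% per group and 26% at 1%. The added burden is small, because each such event already has to be notified to the sponsor and the ethics committee.
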